- Signing of the ICF should be done before any visit related procedures are performed.
- Body temperature will be measured preferably via the oral route, or in accordance with the local standard of care.
- Investigator must check for acute illness or body temperature $\geq 38.0^{\circ}\text{C}/100.4^{\circ}\text{F}$ at the time of vaccination. If any of these events occur within 24 hours prior to the planned vaccination, the vaccination can be rescheduled as long as this is within the allowed window.
- Information to be collected for targeted physical examinations and vital signs is specified in Section 8.2
- For the booster vaccination visit, blood samples should be taken except when the previous sample for assessment of humoral immunogenicity occurred within 5 days of the visit. If a scheduled visit falls within the PB 1 + D28 visit window (±7d), the PB 1 + D28 visit may be combined with the scheduled visit, and any blood samples that are listed in both visits should only be collected once.
- Whole blood samples (~2mL) will be used for immediate measurement of a platelet count (as part of a complete blood count, if applicable) in a local laboratory or substitute for local laboratory, depending on local feasibility towards turnaround time of sample processing. Serum (4 mL) and plasma (2.5 mL) samples will be derived from the whole blood samples (8 mL and 5 mL, respectively) for retrospective coagulation related testing in a central laboratory in case of a suspected AESI (see Section 10.2, Appendix 2). Unused samples may be used for immunogenicity testing. If a whole blood sample has been taken within 5 days before vaccination, sample collection does not need to be performed before vaccination.
- Solicited AEs (reactogenicity) and unsolicited AEs will be assessed from time of vaccination until 7 days post vaccination and 28 post vaccination, respectively.

- j. If an event is ongoing 7 days post vaccination, the participant should keep filling in the diary until resolution and the diary may be reviewed again at the next visit.
- k. Each participant will be asked at least twice a week, through the eCOA, if they have experienced any new symptoms or health concerns that could be related to infection with SARS CoV 2. Refer to Section 1.3.4 Procedures for Participants with (Suspected) COVID 19. In addition, participants will be asked daily within the 30 day time period post vaccination if they have experienced any health concerns related to suspected AESI's, and if so, participants will be advised to contact the study center. Refer to Section 1.3.4 Adverse Events of Special Interest
- l. All SAEs related to study procedures or non investigational sponsor products will be reported from the time a signed and dated ICF is obtained until the end of the study/early withdrawal. MAAE are to be reported for all participants from the moment of the vaccination until 6 months after vaccination or end of study duration, whatever comes first, except for MAAEs leading to study discontinuation which are to be reported until completion of the participant's last study related procedure. New onset of chronic diseases will be collected as part of the MAAEs. See Section 8.3.1 for more details.
- m. Refer to Section 6.8 for collection and recording of concomitant therapies.
- n. Approximately 0.5 mL of colostrum or approximately ≥ 5 mL of breast milk will be collected if participant is breastfeeding. Collection of breast milk and colostrum is optional.
- o. Investigator must check if the participant has received another COVID 19 vaccine outside the study (eg, national immunization program). If so, the participant is not allowed to receive the booster dose
- p. Participants will be asked to confirm whether subjective changes in (postpartum) breast milk production (reduction) have been noticed (yes/no) and report changes daily in the eCOA diaries.

AE adverse event; AESI adverse event of special interest; D day(s); ICF informed consent form; MAAE medically attended adverse event; PB post booster; SAE serious adverse event; SARS CoV 2 severe acute respiratory syndrome coronavirus 2.

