Visit Type	Screening	Vaccination	Safety	Safety	Safety Immuno	Phone Call for Safety follow-up	Safety Immuno	Safety Immuno	Safety Immuno	Safety	Early exit
Investigator's assessment of reactogenicity (participant's diary)			● ⁵								
Unsolicited AE collection ^f		-----Continuous-----									
Investigator's assessment of reactogenicity (participant's diary)			● ⁵								
(Suspected) COVID-19 surveillance (symptom check) ^g		-----Continuous-----									
Adverse maternal, fetal outcomes		-----Continuous-----									●
AE/SAE/AESI/MAAE recording ^h		-----Continuous-----									●
Concomitant medications ⁱ		-----Continuous-----									●
Delivery history ^j							●				
Safety Sampling											
Laboratory assessments, ~ 6.5 mL ^k	● [#] (~6.5 mL)	● ¹ (~6.5 mL)	● (~6.5 mL)	● ^{cc} (~6.5 mL)	● ^{cc} (~6.5 mL)		● (~6.5 mL)	● (~6.5 mL)			
Whole blood, 12.5 mL ^w Sample will be separated: Plasma sample, 5 mL ^w , Serum, 7.5 mL ^w		● ¹ (5 mL), (7.5 mL)	● (5 mL), (7.5 mL)		● (5 mL), (7.5 mL)		● (5 mL), (7.5 mL)	● (5 mL), (7.5 mL)			
Other sampling											
Humoral immunogenicity sample (serum) ^l		● ¹ (10 mL)			● (10 mL)		● (10 mL)		● (10 mL)		
N-serology sample		● ¹ (2.5 mL)			● (2.5 mL)		● (2.5 mL)		● (2.5 mL)		
Colostrum and breast milk sample, mL (optional) ⁿ							● colostrum 0.5 mL	● breast milk, ≥5 mL			
Vaccination-related biomarker blood sample (PAXgene [®] tubes, 2.5 mL)		● ¹ (2.5 mL)			● (2.5 mL)		● (2.5 mL)				
Cellular immunity (PBMC) blood draw Subset of approximately 25 participants per group, if feasible (optional) ^{dd}		● ¹ (30 mL)			● (30 mL)		● (30 mL)				

Monthly phone calls are intended for safety follow up and delivery planning, should start after Day 29 and continue until birth; #optional laboratory assessments at screening to be done at the discretion of the investigator.

¹ pre dose; ²pre and post dose; ³Screening diagnostic tests for current SARS CoV 2 infection can be performed. ⁴SARS CoV 2 test is to be repeated pre vaccination on Day 1 only if the test at screening was not done or was done more than 4 days before Day 1 visit. ⁵ local and systemic solicited AEs should be verified and reported in eDC according to the toxicity

grading scale. If an event is ongoing 7 days post vaccination, the participant should be encouraged to continue filling in the diary until resolution and the rest of the diary may be reviewed again at the next visit.

Footnotes:

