- a. Screening can be performed within 28 days prior to the study vaccination or on the day of vaccination. If screening is performed on the day of vaccination (recommended), Visit 1 and Visit 2 will coincide on Day 1. In that case, laboratory assessments should only be done once. During the screening visit, at least, all eligibility criteria must be verified prior to randomization and vaccination.
- b. If allowed by local regulations: study visits may take place at the participant's home or other location in the event of an ongoing SARS CoV 2 infection performed; visits can be performed by a trained health care professional (HCP) via phone call or a telemedicine contact.
- c. For those participants who are unable to continue participation in the study until the end of study visit, but for whom consent is not withdrawn, an early exit visit will be conducted as soon as possible. Participants who wish to withdraw consent from participation in the study will be offered an optional visit for safety follow up. For these participants only the safety assessments of the early exit visit (no blood sampling for immunogenicity) will be performed.
- d. Postpartum (PP) 1 refers to the day of pregnancy completion/termination. Visit 9 (PP 1) should occur on the day of pregnancy completion/termination or within 3 days after pregnancy completion/termination. Assessments collected the day before birth can be used, but are preferably collected on the date of birth. If the delivery takes place in a hospital where the site staff does not have privileges, it is expected that medical records are obtained to collect the applicable protocol required safety information. Blood samples are not expected in this case.
- e. Signing of the ICF should be done before any study related procedure. The ICF can be signed remotely prior to the Screening Visit. By signing the main ICF, consent is also given to follow up the neonates/infants after birth. Note: Logistics such as downloading of an application to the participant's eDevice, or accessing study materials for enrollment, are not considered a study related procedure.
- f. Check clinical status again before study vaccination.
- g. Maternal demographic information to be collected at screening includes age, race/ethnicity, and geographical location/residence.

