- z. In the situation of a completion/ termination of the pregnancy before the completion of the applicable Study Period visits, PP1 (Visit 9) is to be completed. The participant should then follow the visits scheduled in the 'Study Period' up to Visit 5 (meaning all scheduled visits in this period except for the monthly phone calls Visits 6 8) AND the 'Follow up' section of the schedule of activities (Visits 10 12). Additional guidance if the pregnancy is completed/ terminated before the pre partum visits are completed is provided in Appendix 10.13.
- aa. Body temperature will be measured preferably via the oral route, or in accordance with the local standard of care.
- bb. History of COVID 19 vaccination (name/manufacturer of the vaccine and date of administration) ≥ 4 months prior to the study vaccine will be reported in the eCRF.
- cc. Laboratory assessments performed at Visits 4 and 5 are optional. If the outcome from the laboratory assessment at Visit 3 show abnormal results that are considered clinically significant, then an on site visit should be performed. In this case, an additional sample should be taken for further assessment 7 days later and until normalization of the readings, at the discretion of the investigator and targeted physical examinations and vital signs should be collected. If the outcome from the laboratory assessment at Visit 3 show normal results, only a safety phone call is required (no physical examinations and vital signs needed).
- dd. With only 1 participant in this subset at the time of writing this Protocol Amendment 7, PBMC sampling will be removed from the study as of Protocol Amendment 7 approval.
- ee. The Follow up safety assessments for adults at the end of the study visit (no.12) may be performed simultaneously with postnatal (PN 12 months) follow up safety visit (no. 14) as feasible.

AE adverse event; AESI adverse event of special interest; COVID 19 coronavirus disease 2019; d day(s); eCOA electronic clinical outcome assessment; eDC electronic data capture; FU follow up; ICF informed consent form; MAAE medically attended adverse event; m months; PBMC peripheral blood mononuclear cell; PP postpartum; SAE serious adverse event; SIC Symptoms of Infection with Coronavirus 19; SARS CoV 2 severe acute respiratory syndrome coronavirus2.

1.3.1.1. Vaccine Naïve Adult Participants (Group 4, Including Sentinel and Safety Cohorts): Booster Vaccination Visits

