- bb. Laboratory assessments performed at Visits 4 and 5 are optional. If the outcome from the laboratory assessment at Visit 3 show abnormal results that are considered clinically significant, then an on site visit should be performed. In this case, an additional sample should be taken for further assessment 7 days later and until normalization of the readings, at the discretion of the investigator and targeted physical examinations and vital signs should be collected. If the outcome from the laboratory assessment at Visit 3 show normal results, only a safety phone call is required (no physical examinations and vital signs needed).
- cc. With only 1 participant in this subset at the time of writing this Protocol Amendment 7, PBMC sampling will be removed from the study as of Protocol Amendment 7 approval.
- dd. The Follow up safety assessments for adults at the end of the study visit (no.12) may be performed simultaneously with postnatal (PN 12 months) follow up safety visit (no. 14) as feasible.

AE adverse event; AESI adverse event of special interest; COVID 19 coronavirus disease 2019; d day(s); eCOA electronic clinical outcome assessment; FU follow up; ICF informed consent form; MAAE medically attended adverse event; m months; PBMC peripheral blood mononuclear cell; PP postpartum; SAE serious adverse event; SIC Symptoms of Infection with Coronavirus 19; SARS CoV 2 severe acute respiratory syndrome coronavirus.

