3. OBJECTIVES AND ENDPOINTS

Objectives	Endpoints
Primary	
To assess the safety and reactogenicity of Ad26.COV2.S administered intramuscularly (IM) as a 1-dose (5×10^{10} vp) schedule in adult participants, during the 2 nd and/or 3 rd trimester of pregnancy, and (potentially) postpartum.	
 • Solicited local and systemic AEs for 7 days after vaccination, or until resolution. • Unsolicited AEs for 28 days after vaccination. • SAEs and AESI throughout the study (from vaccination until end of the study, ie, at least 12 months after delivery). • MAAEs until 6 months after vaccination. • AEs leading to study discontinuation (during the entire study).
To assess the humoral immune response in peripheral blood of adult participants to Ad26.COV2.S administered IM as a 1-dose (5×10^{10} vp) schedule, during the 2 nd and/or 3 rd trimester of pregnancy, 28 days after vaccination.	
 • Serological response to vaccination as measured by ELISA; [S-ELISA, EU/mL]), 28 days after vaccination.
Secondary	
Adults	
To assess safety of the booster dose of Ad26.COV2.S at 5×10^{10} vp on participants who were vaccine naïve at study entry.	
 • Solicited local and systemic AEs for 7 days after booster vaccination, or until resolution. • Unsolicited AEs for 28 days after vaccination. • SAEs and AESI throughout the study (from vaccination until end of the study, ie, at least 12 months after delivery). • MAAEs until 6 months after vaccination. • AEs leading to study discontinuation (during the entire study).
To assess pregnancy outcomes in adult participants who have received Ad26.COV2.S during the 2 nd and/or 3 rd trimester of pregnancy.	
 • Pregnancy outcomes (including, live term birth, live preterm birth, stillbirth, and abortion) (non-exhaustive).
To assess pregnancy-related AEs in adult participants who have received Ad26.COV2.S during the 2 nd and/or 3 rd trimester of pregnancy.	
 • Pregnancy-related AEs throughout pregnancy (including gestational diabetes, gestational hypertension, premature rupture of membranes, premature labor, premature uterine

	contractions, poor or restricted fetal growth, pre-eclampsia, eclampsia, vaginal or intrauterine hemorrhage) (non-exhaustive).

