- In the situation of a completion/termination of the pregnancy before the completion of the applicable Study Period visits, the participant should follow the visits scheduled in the ‘Study Period’ (except for the Monthly phone calls) AND the ‘Follow-up’ section of the schedule of activities.
- If the pregnancy is completed/ terminated before the completion of the Day 29 it should be judged based on the participants health and safety if these visits can be performed. These visits are associated to our primary objective and therefore of high interest to be completed.
- If the delivery takes place in a hospital where the site staff does not have privileges, it is expected that medical records are collected to collect the applicable protocol required information.

Randomization	General timing of birth	Detailed timing of birth	Guidance for completion of visits	Protocol language		
1-dose schedule	Birth before completion Study Period visits Vaccination 1	Before start visit window of Day 29	Day 8	If not yet performed, visit can be skipped. Please perform diary review with participant as soon as feasible (phone is acceptable)		
			Day 15			
			Day 29			
					Monthly phone calls	Not applicable
			During visit window of Day 29	Day 29	If not yet performed, visit can be skipped, provided that PP1 has occurred. If Day 29 nor PP1 visit were performed, Day 29 is recommended to be performed as soon as possible based on assessment of participant health, as long as it does not overlap with the window of the next scheduled visit.	
				Monthly phone calls	Not applicable	
			After Day 29	Monthly phone calls	Not applicable	

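### Two visit rules conflict with the Day 29 blood draw and, followed literally, can leave a participant without serum for the primary S-ELISA endpoint

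*Protocol*

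**What the plan says.** Protocol Section 3 gives the primary immunogenicity endpoint as "Serological response to vaccination as measured by ELISA; [S-ELISA, EU/mL]), 28 days after vaccination". Day 29 VNA is secondary. In both adult schedules (Sections 1.3.1 and 1.3.2), Visit 5 is Day 29 ±7 days, typed as a safety and immunogenicity visit. Its column holds a 10 mL humoral serum, a 2.5 mL N-serology sample, a PAXgene tube and 12.5 mL of whole blood for plasma and serum.

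**Phone-call rule.** Footnote cc in Section 1.3.1 opens with "Laboratory assessments performed at Visits 4 and 5 are optional". It ends by saying that if the Visit 3 laboratory results "show normal results, only a safety phone call is required (no physical examinations and vital signs needed". Footnote bb in Section 1.3.2 carries the same rule for Groups 1-3: "only a safety phone call is required (no physical examinations and vital signs needed".

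**Skip rule.** Section 10.13 (Appendix 13), for birth during the Day 29 window, says of the Day 29 visit: "If not yet performed, visit can be skipped, provided that PP1 has occurred". Footnote d in both schedules covers delivery in a hospital where site staff have no privileges. Records are to be obtained, and "Blood samples are not expected in this case". Footnote z in Section 1.3.1 (footnote y in 1.3.2) addresses women whose pregnancy ends early: "The participant should then follow the visits scheduled in the" study period, up to Visit 5. Appendix 13 itself says that these visits serve the primary objective and matter for that reason.

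**The concern.** A telephone call yields no serum. Footnotes cc and bb name Visit 5 and make no exception for its immunogenicity draws, so a site working from the words could close Visit 5 by phone.

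The Appendix 13 skip depends on PP1 having happened, not on blood having been taken there. Combined with footnote d, a woman can comply with every written rule and have neither a Day 29 nor a PP1 serum. She then contributes nothing to the Day 29 S-ELISA or VNA summaries. The stored safety serum is no back-up, because in both schedules it is drawn at the same visits. Enrollment is ceasing, so a lost sample cannot be replaced by a further participant.

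**Working it through.** **1. Is a Day 29 draw planned for everyone?** Table 1 (Section 8) allows this to be checked against the schedule.

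- Humoral draws in the schedule: Day 1, Day 29, PP1, PP 6 months = 4. Table 1 also says 4.
- Table 1 total without PBMC: 6.5×7 + 10×4 + 2.5×4 + 5×5 + 7.5×5 + 2.5×3 = 45.5 + 40 + 10 + 25 + 37.5 + 7.5 = 165.5 mL, as stated.
- Dropping only the optional safety laboratory samples at Visits 4 and 5: 165.5 − 2×6.5 = 152.5 mL. The table allows for this, because it marks the laboratory row as a maximum of 7.
- Dropping all blood at both visits: 165.5 − 13 − 10 − 2.5 − 5 − 7.5 − 2.5 = 125.0 mL. Humoral samples fall from 4 to 3, and none of the three left is defined as 28 days after vaccination.

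Table 1 is headed as a maximum, so it shows that the draw is planned, not that it is compulsory. It fits a reading in which only the safety laboratory samples are optional. It does not fit Visit 5 as a phone call.

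**2. Footnotes cc/bb against the rest of the protocol.** Section 8.2.1 lists a targeted examination at Day 8 and Day 29, not Day 15, whereas the footnote waives examinations at a visit pair that includes Day 29. Sections 4.1 and 8.1.1 take humoral samples from all adult participants. The passages do not agree.

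**3. Appendix 13 and footnote d.** The Day 29 window is 29 ± 7 = Days 22-36, that is, 21-35 days after the dose. For a birth in that window:

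| PP1 | Day 29 under the rules | Serum near Day 29 |
|---|---|---|
| Done, blood drawn by Day 36 | may be skipped | yes, from PP1 |
| Done, blood drawn after Day 36 | may be skipped | outside the window |
| Done from records, no blood | may be skipped if this counts as PP1 | none |
| Not done | recommended, health permitting, if clear of the next visit's window | only if the advice is followed |

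The second row is possible because PP1 may take place up to 3 days after birth: births on Days 34, 35 and 36 allow PP1 as late as Days 37, 38 and 39.

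**4. Can birth fall in the window?** Eligibility runs from week 16 to week 38 at vaccination. Gestational age at birth is not fixed by the protocol, so it is assumed here. Subtracting 3 to 5 weeks, birth at week 37, 40 or 41 implies vaccination at weeks 32-34, 35-37 or 36-38. All lie in the eligible range, so the case is foreseeable.

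**5. How many sera?** The protocol gives no count of births in the window, of skipped Day 29 visits or of deliveries where staff lack privileges. No loss can be computed. For scale only, if a share f of sera were missing, the confidence interval of the log geometric mean would widen by a factor of about 1/√(1−f): 5% at f = 0.10, 15% at 0.25, 41% at 0.50. These are assumed values of f, not forecasts.

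**The case against.** The best defence of footnotes cc/bb is their position and wording. The marker sits only on the safety laboratory cells at Visits 4 and 5. The cells for humoral serum, N-serology, PAXgene and plasma/serum do not carry it. The parenthesis waives examinations and vital signs and never mentions immunogenicity. The repeat sample is due 7 days after Visit 3 (Day 8), which is Day 15, or Visit 4, and that visit has no other blood draw. This stands. A reader might infer that the protocol waives the Day 29 serum for everyone with normal Visit 3 results. The documents do not support that. The footnote is a loosely worded contradiction, probably meant for Visit 4.

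For Appendix 13, the defence is that PP1 carries its own 10 mL humoral serum, usually inside or near Days 22-36, so the skip normally substitutes one sample for another. The appendix also recommends Day 29 where neither visit was done, and a records-only delivery could be read as PP1 not done. Footnote z refers to the appendix for further guidance. This also largely stands. It does not close the gap: the condition is tied to the visit and not to blood, the fallback is only a recommendation, and nothing says how a records-only PP1 counts.

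The study is descriptive, so no test depends on complete Day 29 data. Whether a PP1 serum is analysed as the Day 29 value is visit mapping that can properly be left to the SAP, and its absence here is no finding.

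**Conclusion.** The inconsistency is real and in the current text. Footnotes cc/bb contradict the Visit 5 column, Section 8.2.1 and the sample count in Table 1. The Appendix 13 skip, read with footnote d, allows a compliant participant to have no serum around Day 29, and it sits badly with footnotes z/y and with the appendix's own remark about the primary objective.

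The size is unknown and likely a small fraction. Loss through Appendix 13 needs three things together: birth in the window, a skipped Day 29, and no usable PP1 blood. A reader might take the share of eligible gestational weeks that places birth in the window as the share of sera lost. It is not: it counts women who may skip, most of whom would have a PP1 sample. The benefit of a change is also limited to women whose Day 29 is still ahead when it takes effect, at most those vaccinated within the preceding 35 days.

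This is a wording repair that protects a primary endpoint, not a defect that undermines the study. The row of Appendix 13 for birth before the Day 29 window is not legible enough in the text available to support any conclusion.

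**What to change.** Reconcile the passages by amendment or site clarification:

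1. **Footnotes cc and bb:** state that the Visit 5 humoral and N-serology draws are due whatever the Visit 3 laboratory results show, or limit the phone-call wording to Visit 4. Bring the Day 29 examination in Section 8.2.1 into line with whichever wording is kept.
2. **Appendix 13, birth in the Day 29 window:** make the skip conditional on a PP1 humoral serum actually drawn on Days 22-36. Otherwise the Day 29 draw is taken.
3. **Footnotes z and y:** add a cross-reference so that they and Appendix 13 state one rule.

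The cost is a few sentences. No sample is added beyond those already in the schedules and Table 1. The treatment of a PP1 serum in the Day 29 analysis can stay with the SAP.
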